## Blood and other Biological Samples

Please create or insert a table describing the proposed collection of blood or other biological specimens. Participants will be asked to use a breathalyzer to determine BAC, and to provide urine samples for drug testing. No blood samples will be collected, although HIV and liver function indicators will be collected from participants' medical records (see assessment table). Participants recruited from CUMC/NYP will sign a "HIPAA Compliant Authorization for Release of Medical Information and Confidential HIV Related Information", so that clinic staff can disclose and collect information from medical records to research team. Participants identified from RecruitMe will be asked to assist in collecting their medical chart

abstracted HIV and liver function indicators from their providers before being scheduled for their baseline sessions.

## Assessment Instruments

Create a table or give a brief description of the instruments that will be used for assessment

Please see attached amended measures/assessment table.

Please attach copies, unless standard instruments are used

## Research Related Delay to Treatment

Will research procedures result in a delay to treatment?

No

Treatment to be provided at the end of the study

Participants will not receive additional intervention at end of study.

After the 90 day follow-up evaluation, if participants are seeking additional treatment, they will be encouraged to speak with social workers at the clinic, and/or will be referred to other alcohol treatment programs in the institution or elsewhere in participant's communities.

## Clinical Treatment Alternatives

Clinical treatment alternatives

There will be two conditions in the trial. One will consist of the in-person Clinician's Guide (tailored for HIV/HCV) with HealthCall. The other is an educational control condition. Other accepted psychosocial methods to treat drinking and alcohol problems are cognitive behavioral therapy, motivational interviewing, and self-help groups such as AA.

## Risks/Discomforts/Inconveniences

Risks that could be encountered during the study period

Data can be linked to participants' identity. Data will not include identifying information and will be identified by a subject ID number only. All data will be entered and maintained in a secured clinical trials electronic database and coded with a unique identifier assigned to each participant. Identifying information linked with subject study ID numbers will be kept in separate secured files in locked cabinets and will be available only to selected clinic and research staff members who need to interact with the participants and/or track study progress. This information will also be available to State and institutional regulatory personnel (who may review records as part of routine audits).

Participants are heavy drinkers. Therefore, it is possible that their drinking may become problematic at some point during the study. However, the intervention (and even the advice/education control condition) is likely to minimize the risk of such an occurrence, as compared with patients not enrolled in the study (who are likely receiving no intervention to decrease drinking). Efforts will be taken to monitor for adverse events and refer participants to needed care, as discussed below.

Participants may experience discomfort during assessment, in responding to questions about alcohol, liver disease, or HIV, perhaps by realizing as a result of the assessment that their drinking is harming their health. However, this is a legitimate concern and during the study such distress may help motivate them to reduce their drinking which will be beneficial to them. We will take steps to minimize the risk of discomfort, but participants will have the option to discontinue participation or skip distressing questions.

Describe procedures for minimizing risks

-Recruitment procedures will ensure that participants understand and agree to the informed consent (e.g., research coordinator or research team member will discuss content, informed consent will include quiz).

-Participants will be informed of alternative treatments for alcohol problems and provided referrals as indicated or requested, and encouraged to speak with their HIV providers and/or social workers at the clinic about their needs, questions, and concerns.

-While every possible step will be taken to minimize risk of discomfort occurring in the first place, consent documentation will make it clear that participants may refuse to continue with the study at any time or may refuse to answer particular questions without penalty.

-The clinical status of participants will be reviewed regularly during weekly supervision of the study counselor with the PI. Any adverse events will be evaluated to determine if the participant should be removed from the study and/or referred for more intensive treatment, and will be promptly reported to the IRB.

-Confidentiality will be protected by various means, including coded records, password protection, encryption of electronic data, and storing signed consent forms in locked cabinets.

## Methods to Protect Confidentiality

Describe methods to protect confidentiality

In the trial, all records will be kept confidential. All paper records and material with identifying information will be kept in a locked filing cabinet at the HIV clinics while participants are involved in the study, and then transferred to a locked filing cabinet in our offices at Psychiatric Institute ([name]). Identifying information (including name and phone number) for all potential participants prior to enrollment will be destroyed if they decide to not complete further screening or are found to not be eligible.

Access to HealthCall on the smartphone is secured with a personal pin number known only to the participant and study personnel (as necessary). After participants complete their daily responses to HealthCall, the information is automatically transmitted in encrypted form, without personal identifiers, to a password-protected server. Study data on this server will only be accessible by the Principal Investigator and study personnel. Access to these data is protected through two levels of login/password security. If data

uploading is not immediately possible because no wi-fi connectivity is available, then uploading is reattempted when wi-fi connectivity becomes available.

HealthCall data consists entirely of numeric codes keyed to alphanumeric indexes that are not of human-readable value. All electronic data from the participants' HealthCall application data entry will be saved to the database without their names or other identifying information.

Electronically stored data from study assessments and other study data will not include identifying information and will be identified by a subject ID number only. The database linking participants' names to IDs will be securely stored and independent of other study databases.

*Will the study be conducted under a certificate of confidentiality?*

Yes, we have already received a Certificate of Confidentiality

## Direct Benefits to Subjects

Direct Benefits to Subjects

Participants in the intervention condition may benefit by decreasing their drinking, as the intervention was adapted from other evidence based, effective interventions. However, it is also possible that they will not benefit from the intervention.

Although the control condition will receive brief advice and educational materials, this will likely not be substantially different than standard-of-care.

## Compensation and/or Reimbursement

Will compensation or reimbursement for expenses be offered to subjects?

Yes

Please describe and indicate total amount and schedule of payment(s).

Include justification for compensation amounts and indicate if there are bonus payments.

Participants will receive round-trip MetroCard at all appointments to compensate travel (value: \$5.50).

Participants will receive compensation in ClinCard payments and will be compensated according to the phase of the study they enroll in and what appointment they attend.

Participants enrolled in the *formative research* will receive a total of \$25 for their one-session commitment.

Participants enrolled in the *pre-test* can earn up to a total of \$95 and a smartphone or \$195.

- \$10 at consent/enrollment

- \$25 at baseline

- \$25 at 30-day assessments

- \$35 and a smartphone or \$135 at 60-day assessments (please see below)

Participants enrolled in the *trial* can earn up to a total of \$180 and a smartphone or \$280.

- \$20 at consent/enrollment
- \$40 at baseline
- \$40 at 30-day assessments
- \$40 and a smartphone or \$140 at 60-day assessments (please see below)
- \$40 at 90-day assessments

Participants in the intervention condition may keep the smartphone used in the study or receive \$100 in ClinCard payment if they choose to return it. Control participants will also be offered either a smartphone or \$100 in ClinCard payment. Intervention participation will not be incentivized, as intervention in clinic settings is not paid.

## Uploads

Upload the entire grant application(s)

Upload copy(ies) of unbolded Consent Form(s)

Upload copy(ies) of bolded Consent Form(s)

Upload copy(ies) of recruitment materials/ads to be reviewed

Upload a copy of Certificate of Confidentiality

Upload copy(ies) of the HIPAA form

hipaa 8-17-18.pdf

Upload any additional documents that may be related to this study

Understanding and Intervening With Heavy Drinking Among Patients With HIV and HCV

ClinicalTrials.gov identifier: NCT03652675

Analysis Plan excerpt copied from K23 grant proposal finalized May 6, 2014

12.3.2.13. Pilot study: Primary analyses. Chi-squared analyses will assess differences between conditions in gender, ethnicity, age (dichotomized by median split), and education (dichotomized by high school graduation status). If any demographics differ, they will be controlled; otherwise no variables will be controlled. The primary outcome will be drinking quantity (mean drinks per drinking day in the last month), consistent with previous studies of HealthCall^{15,64,92}. Other drinking outcomes (drinking frequency, maximum quantity, frequency of binge drinking) will also be evaluated. I will determine if drinking decreases differentially between the two conditions using mixed effect GLMs, specifying any non-normal (e.g. Poisson) distributions of the outcomes as needed. Power. The sample size (n=45; assuming 75% retention¹⁵) is adequate for detecting large differences (d=0.85) with 80% power. However, as moderate effects were previously found for MI+HealthCall [d=0.44]¹⁵, a moderate effect *even if not significant* would indicate promise for a full trial.

12.3.2.14. Pilot study: Secondary analyses. Interactions. Because previous work found MI+HealthCall to be particularly effective with alcohol dependent patients¹⁵, the sample will be dichotomized by alcohol dependence (AD; DSM-IV)¹¹⁶, and alcohol use disorder (AUD; DSM-5)¹¹⁵ status. To determine if efficacy differs by AD or AUD, I will conduct GLMs for 60-day drinking quantity, with condition, AD or AUD, and their interaction as predictors. Based on previous work at this clinic, ~50% of patients will have AD, with AUD prevalence higher, given the lower threshold. Interactions with gender and ethnicity will also be explored. Changes in readiness to change and self-efficacy. I will assess differential group change in readiness to change and self-efficacy using mixed effect GLMs. Power. I will be able to detect large interaction effects (f=0.52) and large group differences in self-efficacy and readiness to change (d=0.85) with 80% power.

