## TRIAL PROCEDURES

### (1) Explanation of the study and consent

Individuals who appear potentially eligible by the CUMC/NYP clinic recruiter's screening of the medical records or screening through database (recruitment method 1 and 2 as described in the recruitment procedures) and report interest in participating will speak briefly with the research coordinator by phone, who will be trained in human subjects' protections and will ask several simple questions to determine inclusion/exclusion criteria. Individuals who call as a self-referral via flyer or provider (recruitment method 3) will call the research coordinator directly to complete this described phone screening. The research coordinator will meet potential participants at the clinic to obtain informed consent and conduct additional screening for alcohol use disorder status (needed for randomization), as well as psychosis, suicidality, and homicidality, and risk of developing alcohol withdrawal symptoms (final exclusion criteria). Participants ineligible due to psychosis, suicidality, homicidality, and/or being at risk of developing alcohol withdrawal symptoms will be immediately brought to the attention of clinic providers so that they can be appropriately managed; will receive brief advice on alcohol reduction, and referral for help with alcohol abuse if desired or clearly indicated. Eligible participants will be scheduled for a baseline session at either the clinic or the NYSPI offices ([name]), pending space constraints.

In order to obtain participants' health information from their medical records, clinic staff advised that their standard practice of disclosing health information requires written authorization from participants in accordance to HIPAA and CUMC procedures. To comply with this requirement, eligible participants who are patients of the CUMC/NYP clinic will sign an authorization form at time of informed consent allowing clinic staff to disclose requested health information from medical records to research team.

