### (2) Randomization

After participants complete the screening assessment, the research team member will be able to determine alcohol use disorder status from the responses. The research team member will provide the counselor or PI with the participant identification number (ID; assigned consecutively) and alcohol use disorder status. The counselor or PI will then randomize participants using pre-determined blocked lists created by a biostatistician, in order to balance treatment groups across alcohol use disorder status (the research coordinator will not randomize in order to remain blind to condition). Randomization lists were generated (in R software) and provided by biostatistician [name] on May 4, 2018.

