-Control condition. At baseline, participants will receive brief advice to decrease drinking and a request to spend 20 minutes in the session, observed by the counselor, reviewing an educational pamphlet on drinking, HIV, and HCV. At 30 and 60 days, participants will be asked about their drinking, and again receive advice to decrease drinking. This condition will provide (a) similar exposure time as CG+HealthCall at baseline, (b) brief counselor contact at 30 and 60 days, (c) the same message to decrease drinking, and (d) access to health information. However, the control condition, a realistic approximation of standard-of-care in many places, does not provide in-depth counselor sessions with feedback informed by liver indicators and HealthCall data, the active components of CG+HealthCall for HIV/HCV. This condition was chosen to indicate if CG+HealthCall for HIV/HCV is an improvement over standard-of-care, an important distinction to determine if it warrants further study and eventual dissemination.

-Assessments will precede counselor sessions, and will occur at baseline, 30 days, 60 days, and 90 days (90 days is assessment-only and includes no counselor sessions for either condition). Assessment questionnaires

will be self-administered electronically with the exception of the Timeline Followback and assessment of alcohol use disorder and dependence, which will be administered by the research coordinator or a research team member. The research coordinator/team member will supervise all assessments and answer questions as needed. Efforts will be made to keep the research coordinator/team member blind to condition to minimize potential bias in assessment.

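### Covariates are picked by chi-squared tests on four demographics, which shuts out baseline drinking; unless baseline means are constrained equal between arms, the condition contrast is less precise than a baseline-adjusted one

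*SAP*

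**What the plan says.** SAP 12.3.2.13 (Primary analyses) sets the covariate rule. "Chi-squared analyses will assess differences between conditions in gender, ethnicity, age (dichotomized by median split"), plus education split at high school graduation. It continues: "If any demographics differ, they will be controlled; otherwise no variables will be controlled". No significance threshold is given for these tests.

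The primary analysis follows: "I will determine if drinking decreases differentially between the two conditions using mixed effect GLMs". The outcome is mean drinks per drinking day in the last month. The SAP does not say whether baseline is one of the repeated outcomes, whether the arms share a baseline mean, or which contrast is primary. The protocol's primary hypothesis concerns levels at 60 and 90 days.

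For the interaction analyses, SAP 12.3.2.14 says: "I will conduct GLMs for 60-day drinking quantity, with condition, AD or AUD, and their interaction as predictors". Baseline drinking is not in that list.

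Both omitted variables are collected. Under Trial Procedures (3), "Assessments will precede counselor sessions, and will occur at baseline, 30 days, 60 days, and 90 days". Under Trial Procedures (1), staff "conduct additional screening for alcohol use disorder status (needed for randomization"), and under (2) the counselor or investigator will "randomize participants using pre-determined blocked lists created by a biostatistician, in order to balance treatment groups across alcohol use disorder status".

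**The concern.** In a randomised trial a baseline imbalance arises by chance, and a test of it says nothing about whether the variable predicts drinking. The rule therefore lets chance choose the model. It also excludes the variable most likely to be prognostic, the baseline value of the outcome itself, and the factor on which randomisation is blocked.

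Precision matters more than usual here. The sample is small, and the SAP does not rely on significance alone. It notes that "as moderate effects were previously found for MI+HealthCall [d=0.44"] and treats a moderate effect as promising even when it is not significant. The spread of the estimate therefore feeds directly into the decision about a full trial.

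**Working it through.** **Inputs.** From the SAP: d=0.85, 80% power, n=45, earlier effect d=0.44. From the protocol: about 1:1 allocation, and 31 participants with at least one session (Overall Progress). The 31 is an upper bound for follow-up, because some were lost after baseline. Assumed, because the documents give no value: two-sided 5% level, and correlation r between baseline and follow-up drinking of 0.3, 0.5 or 0.7.

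**1. The plan's own figure.** A two-group t comparison with 23 and 22 per arm has 79.6% power at d=0.85, so the stated 80% reproduces as an unadjusted follow-up comparison. A one-sided test gives 87.7% and does not reproduce it.

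**2. Variance of the condition contrast**, relative to follow-up only (=1), with equal variances, complete data and a linear model:

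- change from baseline (baseline as an outcome, separate arm means): 2(1−r)
- baseline-adjusted (or, nearly, a common baseline mean): 1−r²
- ratio of change to adjusted: 2(1−r)/(1−r²) = 2/(1+r) = 1.54, 1.33, 1.18
- ratio of follow-up only to adjusted: 1/(1−r²) = 1.10, 1.33, 1.96

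Both ratios exceed 1 whenever r lies between 0 and 1. A four-visit simulation (40,000 trials, compound symmetry) gave 1.52, 1.32, 1.17 at day 60 for separate against constrained baseline means at n=45, and much the same at n=31. With a log link (lognormal outcome, exchangeable GEE, two visits, assumed coefficient of variation 0.5–1.1) the ratios were 1.49–1.52, 1.30–1.33 and 1.16–1.17. A Poisson random-effects model was not fitted.

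**3. Power at d=0.85.** Noncentral t; n−4 degrees of freedom for the adjusted model, n−2 otherwise.

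| n | analysis | r=0.3 | r=0.5 | r=0.7 |
|---|---|---|---|---|
| 45 | change | 65% | 80% | 95% |
| 45 | adjusted | 83% | 89% | 97% |
| 45 | follow-up only | 80% | 80% | 80% |
| 31 | change | 49% | 63% | 84% |
| 31 | adjusted | 67% | 75% | 89% |
| 31 | follow-up only | 63% | 63% | 63% |

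To reach 80%, the change contrast needs r of about 0.51 at n=45 and 0.67 at n=31. The adjusted contrast needs about 0.12 and 0.58.

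**4. Chance of a promising estimate under no effect.** The standard error for follow-up only is √(1/23+1/22)=0.298 at n=45 and √(1/16+1/15)=0.359 at n=31. Example at n=31, r=0.5: change 0.359×√1=0.359, z=0.44/0.359=1.22, 11%; adjusted 0.359×√0.75=0.311, z=0.44/0.311=1.41, 8%. Across r=0.3/0.5/0.7 the chance of an estimate of 0.44 SD or more is:

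- n=31: 15/11/6% (change), 10/8/4% (adjusted)
- n=45: 10.6/7.0/2.8% (change), 6.1/4.4/1.9% (adjusted)

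**5. What the demographic rule does.**

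- *Change contrast.* With complete data and a linear model, a demographic main effect cannot alter the 60-day contrast. REML fits to one simulated data set gave −0.404261 (SE 0.3039) with no covariate, with gender, and with gender plus AUD.
- *Follow-up only.* A two-category factor flagged at an assumed 5% level has squared correlation with arm of at least 3.84/n. If it is not prognostic, variance rises by at least 1/(1−3.84/45)=1.09, or 1/(1−3.84/31)=1.14.
- *Chance of a flag.* Permuting arm over the gender and race margins in Sample Demographics, at least one test falls below 0.05 in about 12% of allocations at n=45 (11–15% as an assumed education split varies from 50% to 80%), and 13–18% for the 31. With Yates correction these are 9–10% and 9–11%.
- *Sparse tables.* Sample Demographics less its footnoted losses gives gender 21/9/1 and race/ethnicity 26/3/2. In each table, crossed with two arms, four of six expected counts are below 5, too sparse for chi-squared.

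**6. AUD stratum.** Simulated at n=45 with 29 AUD and 16 non-AUD, stratified blocks of 4 (split and block size assumed), and AUD explaining 10/20/30% of variance. Type I error without AUD is 3.8–4.1/2.7–2.9/2.0% for follow-up only, 4.6–4.9/4.1–4.6/4.1–4.6% baseline-adjusted, and 4.8–5.3% for change, where including AUD makes no difference. Adding AUD to the baseline-adjusted model gains 0 to 3 points of power.

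**The case against.** The strongest reply is that the precision loss comes from an unstated parameterisation, not from the quoted rule. A mixed model with a common baseline mean is compatible with controlling no variables, and the fix below does not make baseline a covariate either. That is right as far as it goes, and it is why the loss is stated conditionally. But the SAP never specifies that model, and both other readings, change and follow-up only, lose precision.

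Further points stand as limits:

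- Against follow-up only, the change contrast is more precise once r exceeds 0.5, so the comparator has to be named: here it is a baseline-adjusted analysis.
- At n=31 the fall from 80% to 63% for the unadjusted comparison is due to accrual. Adjustment decides whether 80% is reached only for r between about 0.58 and 0.67, and at r=0.7 it moves power only from 84% to 89%.
- The 9% and 14% variance inflation and the conservative type I error without AUD apply to follow-up only. They cannot be added to the cost of the change contrast.
- The invariance result needs complete data and a linear model, while the protocol reports loss to follow-up and the SAP allows non-normal outcomes.
- The gain from adding baseline drinking to the interaction models, which the protocol treats as exploratory, was not quantified.

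None of these supports keeping a test-based rule that is inert on one reading and can only be triggered by chance imbalance on another.

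**Conclusion.** The concern holds and should be fixed; confidence is medium. Read literally, the SAP excludes baseline drinking and the AUD stratum as covariates and leaves the primary model's treatment of baseline open. If baseline enters with separate arm means, the contrast has 18% to 54% more variance than a baseline-adjusted one for r from 0.7 down to 0.3. The stated 80% power at n=45 is then missed if r is below about 0.51.

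The cost is precision, not bias, and no type I error inflation from the selection rule is claimed. The stated power is correct for an unadjusted comparison. Omitting AUD is a matter of consistency with the design, with a small cost. The sizes rest on assumed r, equal variances and complete data.

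**What to change.** Replace the covariate rule in SAP 12.3.2.13 with one model, for example:

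> The primary mixed effect GLM has drinks per drinking day at baseline, 30, 60 and 90 days as the outcome, with visit, condition-by-visit terms at 30, 60 and 90 days only (baseline means constrained equal between conditions), and the AUD randomisation stratum. The 60-day and 90-day condition contrasts are estimated from this model. Baseline characteristics are described, not tested, and no covariate is chosen by a baseline test.

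Compared with entering baseline as a covariate, this keeps participants seen only at baseline in the model and avoids choosing a covariate scale under a log link. In SAP 12.3.2.14, add baseline drinking to the 60-day interaction GLMs, log-transformed if a log link is used.

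The cost is SAP wording and one or two degrees of freedom; no new data are needed. Data collection is complete, so the model should be dated and labelled as specified after data collection in any case. The protocol's Summary of Experiences to Date says the data are not yet analysed, while its Status entry says analysis is ongoing. If analysis had begun, report the new model beside the one now in the SAP.

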## Lay Summary of Proposed Research

Among patients with HIV, especially those also infected with HCV, heavy drinking is associated with significant risks to health. However, little is known about how to best intervene with co-infected heavy drinkers, a particularly high risk group for whom targeted intervention has not been developed. Therefore, I propose to test a newly developed drinking-reduction intervention for patients with both HIV and HCV, which combines components of successful interventions developed for HIV and for liver disease patients.

We will recruit 80 HIV/HCV co-infected drinkers from HIV primary care in order to ensure 60 eligible and enrolled trial participants, which should yield an adequate final sample size of 45 participants completing the study. Participants will be randomly assigned to an intervention or control condition, while ensuring that equal numbers of individuals with alcohol use disorder are assigned to each condition. The intervention condition will receive brief in-person sessions with a counselor and will be asked to use a smartphone app daily to keep track of drinking and other health behaviors for two months. The intervention sessions will include information about HIV, HCV and alcohol, and the counselor will give the participant information about their liver function and alcohol use to try to motivate them to drink less. The control condition will simply be asked to drink less and will be given pamphlets with general information on HIV, Hepatitis C, and drinking from educational websites on HIV/HCV co-infection. We will then evaluate whether the intervention condition was more effective at reducing drinking than the control condition.

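### Allocation is balanced on alcohol use disorder status, but the primary and other drinking-outcome models exclude it, which makes level comparisons conservative if the disorder predicts drinking

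*SAP*

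**What the plan says.** **Design.** Protocol, Trial Procedures (2) Randomization, says allocation uses "pre-determined blocked lists created by a biostatistician, in order to balance treatment groups across alcohol use disorder status". Section (1) has AUD status assessed at the post-consent screening because allocation needs it. The Lay Summary gives the purpose as "ensuring that equal numbers of individuals with alcohol use disorder are assigned to each condition". Block sizes and the layout of the lists are not described. The lists are dated May 2018.

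**Analysis.** The SAP is an excerpt from a grant proposal finalised in May 2014 and does not mention stratification.
- **Primary and other drinking outcomes (12.3.2.13).** The arms are compared on gender, ethnicity, age and education, and then: "If any demographics differ, they will be controlled; otherwise no variables will be controlled". The model statement is "I will determine if drinking decreases differentially between the two conditions using mixed effect GLMs".
- **AUD and dependence interactions (12.3.2.14).** "I will conduct GLMs for 60-day drinking quantity, with condition, AD or AUD, and their interaction as predictors". The AUD version of this model does contain the randomisation factor.
- **Readiness and self-efficacy (12.3.2.14).** Mixed-effect GLMs, with no covariates named.

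**Hypothesis.** The protocol's Primary Hypothesis is worded in levels: drinks per drinking day lower in the intervention arm at 60 and at 90 days.

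**The concern.** When allocation is balanced on a factor that predicts the outcome, variation between the levels of that factor largely drops out of the true sampling error of the arm difference. A model without the factor still counts that variation as residual noise. The reported standard error and p-value are then too large and some power is lost.

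The trial has little power to spare. The plan was for 45 completers, and the Overall Progress section reports 31 participants with at least one study session.

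The question is separate from the handling of demographics and baseline drinking. AUD is already used in the allocation, so including it need not depend on a test of baseline balance.

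**Working it through.** **1. Inputs**

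| Input | Value | Source |
|---|---|---|
| Number analysed | 60 × 0.75 = 45 | Protocol, Sample #3; SAP 12.3.2.13 |
| Effect size, power | d = 0.85, 80% | SAP 12.3.2.13 |
| Allocation | about 30 per arm | Protocol, section (3) |
| Alpha | 0.05 two-sided | assumed; not stated |
| AUD prevalence | 70% (50% in a second run) | assumed; the SAP says only that it exceeds the roughly 50% with dependence |
| R², share of outcome variance explained by AUD | 5%, 10%, 20% | assumed; not in the documents |

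To make R² concrete: R² = p(1−p)δ², where p is AUD prevalence and δ is the AUD gap in outcome SDs. At p = 0.70, δ = √(R²/0.21) = 0.49, 0.69 and 0.98 SD.

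**2. The plan's own figure.** The SAP says the sample "is adequate for detecting large differences (d=0.85) with 80% power". An unadjusted two-group comparison of 22 against 23 gives 79.6% by noncentral t, and 81.4% by the normal approximation. The stated figure reproduces, and it is a comparison of two levels.

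**3. Level comparison at one visit, balance on AUD retained.**
- Overstatement of the standard error without AUD: 1/√(1−R²).
- True type I error without AUD: 2 × [1 − Φ(1.96/√(1−R²))]. At R² = 0.10, 1.96/√0.90 = 2.066, which gives 3.9%.
- Power at n = 45 and d = 0.85, simulated with normal outcomes and 70% AUD.

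| R² | SE overstated by | True type I error | Power without AUD | Power with AUD | Loss (points) |
|---|---|---|---|---|---|
| 0.05 | 3% | 4.4% | 78.9% | 81.1% | 2 |
| 0.10 | 5% | 3.9% | 79.8% | 83.8% | 4 |
| 0.20 | 12% | 2.8% | 80.2% | 87.2% | 7 |

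Simulated type I error without AUD agrees (4.4%, 3.9%, 2.8%). With AUD it is about 5%. A second simulation, with permuted blocks of four (size assumed) and 50% AUD, gave 79.8 vs 81.4%, 80.5 vs 83.5% and 81.8 vs 87.6%, so losses of about 2, 3 and 6 points. At R² = 0 nothing is lost.

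**4. Baseline drinking also in the model** (n = 45, within-person correlation 0.3 or 0.5, R² 0.10 or 0.20). Power without vs with AUD ran from 88.8 vs 89.9% to 82.4 vs 87.1%. A separate run at correlation 0.5 gave differences of −0.2 to +2.8 points. Overall the loss is about 0 to 5 points.

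**5. Pure change contrast, constant AUD effect.** AUD cancels from within-person change. At R² = 0.10, power was 65.4 vs 65.1% (correlation 0.3) and 79.4 vs 79.5% (correlation 0.5). If the AUD gap shrinks by 30% by follow-up, the difference is −0.7 to +0.9 points.

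**6. Achieved sample.** With 31 analysed (15 vs 16), unadjusted power for d = 0.85 is 62.8%. The 31 are people with at least one session, so the number at 60 or 90 days may be smaller. I give no separate loss for this size.

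**The case against.** **The SAP's contrast is a change.** It asks whether drinking decreases differentially, and step 5 shows that omitting AUD then costs about nothing if the AUD effect is constant. This stands, and it limits the point. It does not remove it, because the protocol's hypothesis and the SAP's power statement are both about levels, and a baseline-adjusted model can still lose up to about 5 points.

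**R² is undocumented.** Nothing in the documents links AUD to drinks per drinking day. This stands, so every power figure is conditional. If AUD is common, a given R² needs a larger AUD gap: at 85% prevalence, R² of 0.10 to 0.20 means 0.89 to 1.25 SD.

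**This is a pilot.** The SAP would treat a moderate effect as promising even without significance, so a slightly large p-value matters less. This stands too. The width of the interval around that effect still matters.

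**Stronger readings the documents do not support.** A reader might infer that the SAP ignores AUD altogether. It does not: 12.3.2.14 models 60-day quantity with AUD as a predictor. A reader might also infer that the primary result would be invalid. The error is conservative, and simulated type I error stays below 5% wherever AUD is prognostic and balance is kept. Nor do the documents show that power is necessarily lost, as steps 4 and 5 make clear.

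**Conclusion.** The mismatch is real and rests on the text: AUD governs allocation, and the covariate rule keeps it out of the primary model and the other drinking-outcome models. For a level comparison at 60 or 90 days with 45 analysed, the cost is about 2, 4 or 7 points of power at an assumed R² of 5%, 10% or 20%, with the test conservative to the same degree. It falls to about 0 to 5 points with baseline drinking in the model. It is about nil for a pure change contrast with a constant AUD effect, and nil if AUD is not prognostic.

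These figures assume normal outcomes, two-sided 5% testing and AUD balance retained among those analysed. Dropout would disturb that balance and reduce the conservatism, and count models may behave somewhat differently. This is an inexpensive improvement in precision and does not threaten validity.

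**What to change.** State in 12.3.2.13, and for the readiness and self-efficacy mixed models in 12.3.2.14, that AUD status as used for randomisation is a pre-specified fixed effect whatever the demographic tests show. Amend the clause that bars all other covariates so that it exempts this factor.

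An AUD-by-visit term may be added for the primary outcome where the model supports it, but should not be required in every model. Over four visits it brings the total for AUD to about four parameters, which is a lot for 31 attenders.

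The cost is one sentence and one degree of freedom per model. AUD status is already needed for every allocation, and the protocol's Summary of Experiences to Date says the data had not yet been analysed, so as of that report the term could be fixed before results are seen. The remaining risk is a sparse stratum: at 85% AUD, 31 × 0.15 ≈ 5 people without AUD across both arms.
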